 - Staged with a planned return for reoperation (such as but not limited to damage control laparotomy or burns surgery) OR
 - Change in operative plan such that during the first procedure it is determined that a reoperation is necessary, even if the patient was enrolled preoperatively
- **Return to theatre:** Each individual patient should only be included in the study *once*. Patients returning to theatre due to complications following earlier surgery can be included, as long as their indexed procedure has not already been included in the CASCADE audit.

You should collect data on consecutive patients operated at your centre during the data collection period. This means that all eligible patients should be included.

Strategies to identify consecutive eligible patients could include:

- *Daily review of elective theatre lists.*
- *Daily review of handover sheets/ emergency admission and ward lists.*
- *Daily review of theatre logbooks (both elective and emergency).*

6. Covariates:

Data will be collected on audit standards and confounding factors for risk-adjusted analyses. These include age, sex, ethnicity, body mass index, American Society of Anaesthesiologists (ASA) grade, relevant comorbidities, smoking status, anticoagulant or antiplatelet use, preoperative blood test values, and preoperative anaemia management. Variables including operative urgency, operative procedure, operative contamination, use of tranexamic acid, intraoperative blood transfusions used, haemoglobin level at transfusion, duration of procedure and post-operative iron therapy will also be collected. Without appropriately adjusting for risk factors, it is likely that any findings would be biased and unable to be appropriately analysed on a national scale. A full list of required data fields is available in **Appendix B**, and on the REDCap database.

7. Outcome Measures and Follow-up:

Primary outcome measure:

- Rates of compliance to pre-, intra-, and postoperative audit standards in reducing risk of postoperative cardiovascular complication.

Secondary outcome measures:

- Incidence of postoperative cardiovascular complications within 30-days of surgery according to the Standardized Endpoints for Perioperative Medicine (StEP) cardiovascular.¹³ (see **Appendix D: Definitions of Key Outcomes**).
- 30-day postoperative blood transfusion rates
- 30-day complication rates defined according to the Clavien-Dindo classification (see **Appendix D: Definitions of Key Outcomes**)

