- 30-day reoperation rates
- Critical care bed days up to 30 days postoperatively
- Length of in-patient stay (days) up to 30 days postoperatively
- 30-day readmission rates
- 30-day bleeding event rates (see **Appendix D: Definitions of Key Outcomes**)
- Length of pharmacological VTE prophylaxis (days) up to 30 days postoperatively.

Follow-up should be performed in line with current routine practice within each hospital settings. No additional telephone, in-person or questionnaire-based follow-up is required. Source data may be acquired from hospital in-patient notes, clinical electronic systems, or outpatient letters.

Prior to collecting data, all collaborators will be required complete the mandatory e-learning modules available from the CASCADE project online hub:
<https://incept.ac.uk/course/view.php?id=7>

These include: (1) CASCADE Patient selection; (2) Clavien-Dindo classification (3) Postoperative cardiovascular complications; (4) Postoperative bleeding complications; (5) VTE pharmacological prophylaxis; (6) Data safety governance; (7) Quiz

8. Data Governance:

Data will be collected and stored online through a secure server running the Research Electronic Data Capture (REDCap) web application,^{27,28} and allows safe anonymised data storage by collaborators across Europe. The service is managed by the Birmingham Surgical Trials Consortium (BiSTC) REDCap system hosted at the University of Birmingham, United Kingdom. The security of the study database system is governed by the policies of the University of

Birmingham. Data management and data security within the BiSTC REDCap will abide by the requirements of the General Data Protection Regulations (GDPR) and any subsequent amendments. Collaborators will be given secure REDCap project server login details, allowing secure data storage on the REDCap system.

No patient data will be uploaded or stored on the REDCap database without prior local permissions. All data should be handled in accordance with local data governance policies, and all paper copies of any data should be destroyed as confidential waste within the centre once uploaded to REDCap. Data collected during the CASCADE study can be used for future analyses at the Study Management Group's discretion.

9. Data Analysis & Sample Size:

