Appendix B: Data Dictionary

Pre-operative Data Fields	Required data (definition / comment)	Suggested source(s)
1. Patient age	Years (whole years at the time of operation)	– Clinical letters / notes
2. Patient sex	Male / Female	– Clinical letters / notes
3. Patient body mass index (BMI)	kg/m² (record to two decimal places)	– Drug charts – Clinical letters / notes
4. Patient ASA grade	Grade I-V (Full ASA classification available at: https://www.asahq.org/resources/clinical-information/asa-physical-status-classification-system)	– Anaesthetic notes
5. Smoking status	Current (≤6 weeks, >6 weeks), Previous, Never	– Admissions clerking – Clinical notes
6. Clinical Frailty scale	1-3 / 4-6 / 7-9 (Full Clinical frailty scale available at: https://www.dal.ca/sites/gmr/our-tools/clinical-frailty-scale.html)	– Admissions clerking – Clinical notes
7. History of cardiovascular disease	Yes (myocardial infarction, angina, congestive cardiac failure, TIA/stroke, hypertension, peripheral vascular disease, atrial fibrillation, VTE, pulmonary embolism) / No If congestive cardiac failure, what is the NYHA: I / II / III / IV	– Admission clerking – Anaesthetic notes – Outpatient letters
8. History of respiratory disease	None / Dyspnoea on exertion or CXR (mild COPD) / Dyspnoea limiting exertion to <1 flight or CXR moderate COPD / Dyspnoea at rest/rate >30 at rest or CXR (fibrosis or consolidation)	
9. History of COPD	Yes / No	
10. History of chronic kidney disease	Yes (I / II / IIIA / IIIB / IV / V) / No	
11. History of liver cirrhosis	Yes / No	
12. History of diabetes mellitus	Yes - Type I / Yes - Type II (diet controlled, tablet controlled, insulin controlled) / No	
13. Active cancer and/or cancer treatment	Yes / No	
14. Inflammatory bowel disease	Yes / No	
15. Previous history of VTE	Yes / No	
16. Management of iron-deficiency anaemia	None / Preoperative iron supplementation / Tranexamic acid / RBC transfusion (If yes: 1, 2, 3, 4, ≥5 units)	
17. Preoperative treatment	Yes (Aspirin, ACEi/ARB, β-blocker, α ₂ agonist, rate controlling CCB, DHP CCB) / No If yes, was medication stopped preoperatively? (No / Yes, stopped preop only / Yes, stopped preop & postop)	– Clinical letters / notes PACS software
18. Preoperative therapeutic anticoagulation	Yes (Low Molecular Weight Heparin (LMWH), Warfarin, Direct acting oral anticoagulants (DOACs)) / No	– Clinical letters / notes PACS software

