2. Critical care bed days (if yes)	Number (days from first post-operative day to day of discharge from critical care. If the patient has not been discharged prior to the end of 30-day follow-up, enter '31').	
3. Postoperative haemoglobin	Not applicable / Available (day 0-1, day 1-3, day 4-6, last prior to discharge) If available, please state value in grams/litre	
4. Postoperative interventions for anaemia	None / iron supplementation / Tranexamic acid / RBC transfusion (If yes: 1, 2, 3, 4, ≥5 units)	
5. Cardiovascular complications within 30 days	None / Myocardial infarction / Myocardial injury / Non-fatal cardiac arrest / Coronary revascularisation / Pulmonary embolism (symptomatic non-fatal / asymptomatic) / Deep venous thrombosis (proximal / distal; if either symptomatic / asymptomatic) / New onset Atrial fibrillation / Stroke (select all that apply) *see Appendix D for definitions Please indicate the POD of the event(s) selected.	• Clinical notes • PACS software
6. Bleeding complications within 30 days	None / Major bleeding / Clinically relevant non-major bleeding *see Appendix D for definitions	
7. Post-operative length of stay	Number (days between from the first post-operative day to day of discharge. If the patient has not been discharged prior to the end of 30-day follow-up, enter '31').	
8. Highest 30-day complication grade	None / Clavien-Dindo Grade I-V (see Appendix D for the full 7-point Clavien-Dindo scale). If grade V, was death cardiac, PE or non-cardiac? (see Appendix D for definitions)	
9. 30-day Reoperation	Yes / No	
10. 30-day Readmission	Yes - planned / Yes- unplanned / No (this applies if patient had died during initial admission) If yes: what is the grade of complication (none, grade I, grade II, grade III, grade IV, grade V)	
11. 30-day postoperative COVID status	None / Preoperative / Postoperative If preoperative: are you still symptomatic (yes/no) and were you vaccinated (no / partial / full)	
12. Haemoglobin on readmission	Not available / Available If available, please state value in grams/litre	
13. Interventions for anaemia at readmission	None / iron supplementation (Oral / Intravenous), blood transfusion (If yes: 1, 2, 3, 4, ≥5 units)	
14. Postoperative outpatient VTE prophylaxis duration	Number (days of pharmacological VTE prophylaxis the patient was discharged home with)	

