 - i. A persistent intraluminal filling defect on contrast venography
 - ii. Non-compressibility of one or more venous segments on B-mode compressionultrasonography
 - iii. A clearly defined intraluminal filling defect on contrast enhanced CT
- b. DVT can be divided in proximal and distal³¹:
 - i. Proximal DVT is defined as DVT in the popliteal vein and/or higher (femoral vein, common femoral vein, iliac vein, vena cava).
 - ii. Distal DVT (calf DVT) is defined as DVT in at least 1 of the 3 major paired veins (posterior tibial, anterior tibial, peroneal) in the calf, below the popliteal vein.
- c. DVT can be also divided in symptomatic and asymptomatic³¹:
 - i. Symptomatic DVT is defined as leg pain and swelling resulting from thrombotic occlusion of a major leg vein. It requires specific investigation and treatment.

- ii. Asymptomatic DVT is defined as DVT detected by screening with ultrasound or ascending venography, and with no associated symptoms (leg pain and swelling).

10. Stroke: Embolic, thrombotic, or haemorrhagic event lasting at least 30 min with or without persistent residual motor, sensory, or cognitive dysfunction; if the neurological symptoms continue for >24hrs, a person is diagnosed with stroke, and if lasting ,24 h the event is defined as a transient ischaemic attack³²

B. Bleeding outcomes

Bleeding is an important safety outcome in studies exploring the use of anticoagulation pharmacological therapies. To ensure consistency across research studies, a validated and clinically relevant classification should be used. In the CASCADE study, we have adopted the definitions of bleeding outcomes recommended by the European Medicines Agency.

Major bleeding³³ is defined as a bleeding event that meets at least one of the following criteria:

- fatal bleeding
- critical bleeding (intracranial, intraocular, intraspinal, pericardial, retroperitoneal, in a non-operated joint, or intramuscular with compartment syndrome)
- clinically overt bleeding (at surgical or extrasurgical site) associated with a decrease in the haemoglobin level of more than 2 g/dL (20 g/l; 1.24 mmol/L) compared with the pre-operative level
- clinically overt bleeding (at surgical or extrasurgical site) leading to transfusion of two or more units of whole blood or packed cells

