IVa	
Life-threatening complications requiring critical care management with single organ dysfunction, or neurological complications including brain haemorrhage and ischemic stroke (excluding TIA).
 
Examples: Single organ dysfunction requiring critical care management, e.g. pneumonia with ventilator support, renal failure with filtration; SAH; stroke

IVb	
Life-threatening complications requiring critical care management with multi-organ dysfunction.

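### Appendix D puts two duration thresholds under 'Stroke' and the outcome form has a single box, so events of 30 minutes to 24 hours may be coded inconsistently and cannot be separated afterwards from that field

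*Protocol*

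**What the plan says.** Appendix D, section A, lists the conditions that count as perioperative cardiovascular adverse events. Item 10, headed Stroke, begins: "Embolic, thrombotic, or haemorrhagic event lasting at least 30 min with or without persistent residual motor, sensory, or cognitive dysfunction". After a semicolon it continues: "if the neurological symptoms continue for >24hrs, a person is diagnosed with stroke". For symptoms shorter than that, "the event is defined as a transient ischaemic attack". The sign before the second 24 h is garbled in the text; the context makes it 'less than'.

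Three other places bear on how such an event is recorded:

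- **Outcome field.** Appendix B, post-operative item 5, ends its list of options with "New onset Atrial fibrillation / Stroke (select all that apply". It asks for the postoperative day of the event but has no TIA option and no duration. The Appendix A form likewise has one 'Stroke' box.
- **Severity grade.** Appendix D, section C, grade IVa covers "neurological complications including brain haemorrhage and ischemic stroke (excluding TIA").
- **Baseline history.** Appendix B, pre-operative item 7, joins the two conditions in one category: "congestive cardiac failure, TIA/stroke, hypertension".

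The definition feeds a secondary outcome in Methods section 7: "Incidence of postoperative cardiovascular complications within 30-days of surgery according to the Standardized Endpoints for Perioperative Medicine (StEP) cardiovascular".

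**The concern.** Under one heading a data collector meets a 30-minute threshold that needs no residual deficit, and then a 24-hour threshold. An event between the two satisfies the first and is named something other than stroke by the second. The form has one box, and the protocol does not say whether such an event belongs in it.

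At stake is what the reported stroke rate means. The Introduction offers the study as benchmarking data for future trials, and Appendix D itself notes that differing definitions obstruct pooling. About 300 centres are expected (Methods section 9), with data gathered by teams of students and junior doctors. If some tick 'Stroke' for a TIA and others do not, the rate mixes two definitions in unknown proportion, and the outcome field cannot be used to undo the mixture.

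**Working it through.** The protocol gives no stroke or TIA rate, so there is no figure of its own to reproduce. The main check is textual.

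**Step 1: apply both clauses of item A.10 by duration.**

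| Duration of event | Opening clause under 'Stroke' | Second clause |
|---|---|---|
| Under 30 min | not met | TIA |
| 30 min to 24 h | met | TIA |
| Over 24 h | met | stroke |

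For inclusion as stroke, the clauses disagree only in the middle row.

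**Step 2: see whether the form settles the middle row.** It does not. Item 5 subdivides pulmonary embolism (symptomatic non-fatal or asymptomatic) and deep vein thrombosis (proximal or distal, symptomatic or asymptomatic), but gives stroke one undivided box. The postoperative day of the event does not reveal how long it lasted.

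**Step 3: see which way the rest of the protocol points.** The second clause and grade IVa both treat TIA as something other than stroke. The baseline field merges the two, but it records history and does not define the outcome. The balance favours the 24-hour reading without stating it as the rule for the box.

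**Step 4: test a bare 24-hour rule for gaps.** Two kinds of event fall through it:

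- A haemorrhagic event resolving within 24 hours would, read literally, be a transient *ischaemic* attack, although grade IVa includes brain haemorrhage.
- A patient who dies of the event before 24 hours never reaches the threshold.

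**Step 5: illustrate a possible size.** The sample of 6000 is from Methods section 9. The rest is assumed: a stroke rate (over 24 h) of 0.3% to 0.6%, and 0.25 to 0.5 TIAs per stroke, with every TIA ticked as 'Stroke' at every centre.

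- Extra events = N × stroke rate × TIA ratio.
  - Low: 6000 × 0.003 × 0.25 = 4.5, or 4.5/6000 = 0.075 percentage points.
  - High: 6000 × 0.006 × 0.5 = 18, or 18/6000 = 0.30 percentage points.
- Standard error of the rate = √(p(1 − p)/N).
  - At 0.3%: √(0.003 × 0.997/6000) = 0.071 points.
  - At 0.6%: √(0.006 × 0.994/6000) = 0.100 points.
- Shift divided by standard error (from unrounded values): 1.06 at the low end and 3.01 at the high end.

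If only half of the TIAs were ticked, the added events would be 2.25 to 9 and the shift about 0.5 to 1.5 standard errors. The full-count figures are therefore the upper range on these assumptions.

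**The case against.** The strongest reply is that item A.10 resolves itself. The opening clause names a broad class of event, and the second clause divides it into stroke and TIA. What the entry calls a TIA is then not a stroke, and grade IVa agrees. This reading is plausible and probably intended. It does not remove the problem, because the broad class is itself what stands under 'Stroke' in the list of outcomes, and the form has one box for it. On the broad reading a TIA may be ticked; on the narrow one it has no box.

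A second reply is training. Methods section 7 makes e-learning mandatory, including a module on cardiovascular complications, and section 11 sets a 100% pass mark. The module's content is not shown. It may standardise coding, but it cannot add a field that the form lacks. Diagnoses written in the clinical notes may also settle many cases.

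A reader might infer that TIAs are in fact counted at some centres and not at others. The protocol shows no difference in practice between centres, so it supports only 'may be coded inconsistently'. A reader might also infer that an uncounted TIA is lost altogether. It is not, because Clavien-Dindo grading takes in all postoperative adverse events, although only the highest grade is recorded. Nor is a 'Stroke' tick without grade IVa a contradiction in itself, since grades follow the treatment required and need not match the diagnosis.

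Finally, the consensus paper and the stroke guideline that the protocol cites are not available here. Whether 30 minutes or 24 hours is faithful to them cannot be judged, and this part of the objection stands.

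**Conclusion.** The definition is ambiguous for events of 30 minutes to 24 hours, and the outcome field cannot separate those events from longer ones afterwards. This follows from the text alone and needs no assumption about rates or behaviour.

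The reach is limited. Stroke is one of the complications in one secondary outcome. The primary outcome is compliance with audit standards, and the major adverse cardiac event composite in Appendix D does not list stroke. It would be wrong to read this as a threat to either.

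The size is unknown. The 4.5 to 18 events in 6000 rest on stroke and TIA rates that the protocol does not supply and on every TIA being counted, so they illustrate a ceiling and are not an estimate. The point is worth correcting because the correction is cheap and makes the reported rate interpretable.

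**What to change.** - **One rule in item A.10.** Reconcile the two clauses by stating when 'Stroke' is ticked. The entry's second clause and grade IVa point to symptoms beyond 24 hours, with TIA not counted as stroke. The study team should confirm this against the consensus definition it says it follows.
- **The gaps.** Say in the same place how haemorrhagic events under 24 hours and deaths before 24 hours are coded, so that a duration rule does not drop them.
- **A separate TIA box.** Add it to Appendix B post-operative item 5, the Appendix A form and REDCap, and report it apart from stroke. Either definition can then be tabulated.

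The cost is a short addition to Appendix D and one extra field, with a possibly lower reported stroke rate. For records already entered without the extra field, separating the two kinds of event may require a return to source notes.

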19. Pre-admission blood tests	Haemoglobin (grams / litre) / Albumin (grams / litre) / Creatinine (ml / min) *Include blood tests taken within the 90 days prior to operation. If multiple blood tests have been taken during this period, record the lowest value. If no pre-admission blood tests are available, please record this as 0.	– Pathology systems
20. Admission blood tests	Haemoglobin (grams / litre) / White cell count (x10 ⁹ / l) / Albumin (grams / litre) / Sodium (mmol/l) / Potassium (mmol/l) / Urea (mmol/l) / Creatinine (ml / min)	– Pathology systems

	*Include the first blood test results from this admission. Only include blood tests taken before surgery	
21. Admission observations	Pulse rate (bpm) / Systolic blood pressure (mmHg) / Glasgow coma scale	–
22. Pre-operative assessment	If elective: Yes (pre-admission anaesthetic assessment clinic) / No. If yes: Did this include pre-operative cardiopulmonary exercise testing (Yes - VO ₂ peak, AT / No). If emergency: Yes (inpatient perioperative or elderly medicine, including physician or nurse specialist) / No	– Clinical letters / notes
23. Preoperative investigations	None / ECG (normal / abnormal) / Echocardiography (LVEF, %) / Coronary angiography	–
Abbreviations: ASA = American Society of Anaesthesiologists; Hb = Haemoglobin; LVEF = Left Ventricular Ejection Fraction PACS = Picture Archiving and Communication.		

Intra-operative Data Fields	Required data (definition / comment)	Suggested source(s)
1. Prior Operations	1 / 2 / >2	
2. Operative urgency (NCEPOD Classification of Intervention)	Immediate (Immediate life, limb or organ-saving intervention - resuscitation simultaneous with intervention. Normally within minutes of decision to operate). Urgent (Intervention for acute onset or clinical deterioration of potentially life-threatening conditions, for those conditions that may threaten the survival of limb or organ, for fixation of many fractures and for relief of pain or other distressing symptoms. Normally within hours of decision to operate) Expedited (requiring early treatment where the condition is not an immediate threat to life, limb or organ survival. Normally within days of decision to operate). Elective (Intervention planned in advance of routine admission to hospital).	– Operative note – Admissions clerking
3. Primary indication	Malignant / Benign If malignant: Primary only / nodal metastases / Distant metastases	– Operative note. – Clinical notes. – Theatre records.

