- Intra-operative complications are not considered unless they have an adverse effect on the patient post-operatively. The only exception to this is intra-operative death; this is classified as grade V.
- All post-operative adverse events are included, even when there is no direct relationship to the surgery.
- All adverse events within the follow-up period (30 days) are included, even after following discharge.
- Diagnostic procedures are not included. For example, a diagnostic oesophagoduodenoscopy (OGD) to look for a source of bleeding without any intervention would not be considered a complication, but a therapeutic OGD with clipping of a bleeding vessel would be considered a grade IIIa complication. Since negative exploratory laparotomies are considered to be diagnostic procedures, they should not be recorded as complications.

Grade	Definition (examples listed in italics)
I	
Any deviation from the normal postoperative course without the need for pharmacological (other than “allowed therapeutic regimens”), surgical, endoscopic or radiological intervention.
 
Allowed therapeutic regimens are: selected drugs (antiemetics, antipyretics, analgesics, diuretics and electrolyte replacement), physiotherapy and wound infections opened at the bedside but not treated with antibiotics.
 
Examples: Ileus (deviation from the norm); hypokalaemia treated with K; nausea treated with cyclizine; acute kidney injury treated with intravenous fluids.

II	
Requiring pharmacological treatment with drugs beyond those allowed for grade I complications. Blood transfusions and total parenteral nutrition are also included.
 
Examples: Surgical site infection treated with antibiotics; myocardial infarction treated medically; deep venous thrombosis treated with enoxaparin; pneumonia or urinary tract infection treated with antibiotics; blood transfusion for anaemia.

IIIa	
Requiring surgical, endoscopic or radiological intervention, not under general Anaesthetic (GA).
 
Examples: Therapeutic endoscopic therapy (do not include diagnostic procedures); interventional radiology procedures.

IIIb	
Requiring surgical, endoscopic or radiological intervention, under GA.
 
Examples: Return to theatre for any reason.

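### The bleeding outcome has no stated onset, no named baseline haemoglobin and no date, so operative loss can make a small postoperative bleed "major" and bleeds cannot be timed against outpatient prophylaxis

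*Protocol*

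**What the plan says.** Bleeding is a secondary outcome, listed in Methods section 7 as "30-day bleeding event rates". Methods section 2 makes the safety of extended thromboprophylaxis a secondary aim, and Appendix D section B presents bleeding as a safety outcome.

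In Appendix D section B, major bleeding "is defined as a bleeding event that meets at least one of the following criteria". Two of the criteria matter here. Both require overt bleeding, at the surgical site or elsewhere. One needs it to be "associated with a decrease in the haemoglobin level of more than 2 g/dL (20 g/l; 1.24 mmol/L) compared with the pre-operative level"; the other needs it to be "leading to transfusion of two or more units of whole blood or packed cells". Section B gives no onset time and does not mention blood lost or units given during the operation.

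In Appendix B, postoperative item 6 is a category, "None / Major bleeding / Clinically relevant non-major bleeding", with no date. Item 5, just above it, asks for the postoperative day of each cardiovascular event. Pre-operative item 19 takes haemoglobin from the 90 days before surgery: "If multiple blood tests have been taken during this period, record the lowest value". Item 20 takes the first value of the admission. Neither is named as the baseline for the bleeding criterion.

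**The concern.** The haemoglobin criterion spans the operation. Its starting point lies before surgery and its end point after it, so the fall includes whatever was lost in theatre. A patient with minor overt wound bleeding on day 2 can therefore be graded major although nearly all of the fall happened on the table.

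The missing date is a separate problem. Appendix B item 14 defines the prophylaxis exposure as the days of treatment the patient was discharged home with. A bleed before discharge comes before that exposure and cannot be caused by it. It may even influence it, since section B itself lists a change in antithrombotic therapy among the features of a non-major bleed. Pooling bleeds from before and after discharge would mix events that could be an effect of outpatient prophylaxis with events that could not.

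An analysis plan cannot recover this later. Local teams make the classification, and the date is never collected.

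**Working it through.** **1. Inputs.** From Appendix D section B: a fall of more than 20 g/L from the pre-operative level, or at least two units. From Appendix B: pre-operative items 19 and 20, intra-operative items 10 to 12, postoperative items 3 to 7 and 14. From Methods section 9: about 300 centres and ten patients a week, over a 14-day period. This reproduces the planned sample, 300 × 10 × 2 = 6,000, which is not in dispute. The documents give no bleeding rate.

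**2. The same boundaries elsewhere in the protocol.**

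| Question | Bleeding | Elsewhere |
|---|---|---|
| Do intra-operative events count? | Not stated | Clavien-Dindo, Appendix D section C: "Intra-operative complications are not considered unless they have an adverse effect on the patient post-operatively" |
| Is the event day recorded? | No (item 6) | Yes, for cardiovascular events (item 5) |
| Which haemoglobin is used? | An unnamed pre-operative level | Two are recorded, under different rules (items 19 and 20) |

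The Clavien-Dindo rule is conditional, and it still counts intra-operative death. It shows that the authors addressed the boundary there, not that a clean exclusion was available to copy.

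**3. The haemoglobin criterion on its most favourable reading.** Suppose every site counts only bleeds that start after surgery. The fall is still measured from before surgery. With isovolaemic replacement, haemoglobin after a loss L from blood volume V is Hb0 × exp(−L/V). The loss that gives a 20 g/L fall is therefore L = V × ln(Hb0/(Hb0 − 20)). With V = 5 L (assumed):

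- Hb0 = 150: 5 × ln(150/130) = 0.72 L
- Hb0 = 130: 5 × ln(130/110) = 0.84 L
- Hb0 = 110: 5 × ln(110/90) = 1.00 L

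With V from 4.2 to 5.6 L and the same starting values, the range is about 0.6 to 1.1 L. An operative loss of this order meets the laboratory half of the criterion. Any later overt bleed that a site regards as associated with the fall then completes it.

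**4. The baseline.** Take 95 g/L as the lowest value in 90 days, 125 g/L on admission and 100 g/L after surgery. From 95 there is no fall (100 − 95 = +5). From 125 the fall is 25 g/L, which qualifies. In general, two baselines disagree for any postoperative value from (lower − 20) up to just under (higher − 20), here from 75 to just under 105. That interval is as wide as the gap between the baselines, so any gap leaves room for opposite classifications.

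**5. What mixing could do to a comparison (illustration only).** Assume true postoperative rates of 2% and 3% (ratio 1.50) and an equal, independent background q of operative events in both groups. Each observed rate is p + q − pq.

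| q | Observed rates | Ratio |
|---|---|---|
| 2% | 3.96% v 4.94% | 1.25 |
| 5% | 6.90% v 7.85% | 1.14 |
| 10% | 11.8% v 12.7% | 1.08 |

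Every rate in this table is assumed. It shows the direction of the effect, not its expected size.

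**The case against.** A reader might infer that ordinary operative blood loss, or two units given in theatre, simply is a major bleed under this text, and that the reported rate would mostly reflect the operation. The documents do not support that.

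- Both criteria need an overt bleed, so a fall in haemoglobin or a transfusion alone does not qualify.
- The item is called a complication, sits among the postoperative fields and under 30-day follow-up on the form, and has a mandatory training module on postoperative bleeding complications.
- Units given in theatre cannot result from a later bleed. The transfusion criterion is affected only if a site treats operative bleeding as the event itself.
- The cohort includes appendicectomy, cholecystectomy and incisional hernia repair as well as transplant and aortic surgery, and no bleeding rate is given.

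These points stand, and they limit the concern to what the text leaves open.

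It can also be said that a bleed must be associated with the fall, which might exclude a trivial ooze. But association does not state how much of the fall must come from the bleed, so sites are left to judge. The baseline example needs a rise of 30 g/L before surgery, and item 6 is coded by the collaborator rather than calculated. Both are true, but the collaborator still has to choose a baseline.

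The definition is said to be adopted from a European Medicines Agency recommendation for consistency across studies. That source was not available, so fidelity to it is not judged. Excluding operative bleeding is partly a trade-off against comparability. An external definition cannot, however, say which of this form's two haemoglobins to use, nor supply a missing date.

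Finally, blood loss, theatre units and serial postoperative haemoglobins are recorded. They allow patients to be flagged in a sensitivity analysis, but they do not date a bleed.

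**Conclusion.** The concern holds as a gap in the outcome definition and in the data collected. Three things are established from the text: no onset is set for a countable bleed, the baseline haemoglobin is not identified, and the bleeding item has no date. It follows that operative loss can raise a small overt postoperative bleed to major, that sites may differ on whether operative bleeding counts, and that bleeds before and after the start of outpatient prophylaxis cannot be told apart. The last consequence matters most for the thromboprophylaxis safety aim, and it does not depend on how the definition is read.

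The size is not known. The 0.7 to 1.0 L figure rests on an assumed 5 L blood volume, isovolaemic replacement and starting values of 110 to 150 g/L. It shows only that the laboratory threshold is within reach of operative loss. How many patients would be reclassified cannot be derived from the documents. The change is worth making because it is cheap and the date cannot be reconstructed later.

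**What to change.** 1. Add the postoperative day to item 6, as item 5 already has. Item 7 gives the length of stay, so the two together place each dated bleed before or after discharge.
2. State in Appendix D section B that the 30-day bleeding outcome counts bleeds beginning after the end of the index operation, and that units given in theatre do not count towards such a bleed.
3. Name one recorded haemoglobin as the baseline for the 20 g/L fall.
4. For the thromboprophylaxis safety aim, analyse bleeds after discharge separately.
5. To keep comparability, also report the adopted definition unmodified.

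The cost is one REDCap field, a few sentences in Appendix D and matching text in the bleeding training module. The headline bleeding rate would be slightly lower. Operative loss stays described by the existing blood-loss and intra-operative transfusion fields, and patient care is not affected.
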